4.4. Withdrawal Criteria

All subjects have the right to withdraw from the study at any point during treatment without prejudice. The investigator can discontinue any subject at any time if medically necessary. It will be documented whether or not each subject completed the clinical study. If study treatment or observations were discontinued, the reason will be recorded and the Sponsor should be notified promptly. The reasons a subject may discontinue their participation in the study could be from one of the following:

- AE
- Death
- Subject withdrew consent
- Physician decision
- Lost to follow-up
- Initiation of protocol-prohibited lipid-lowering therapy (eg, an approved PCSK9 inhibitor)

The applicable reason above will be recorded in the eCRF. It is imperative to obtain complete follow-up data for all subjects whether or not they receive their assigned treatment or have discontinued investigational product. All data collected up until the time of subject withdrawal is to be entered into the eCRF. In addition, every attempt should be made to collect follow-up information except for those subjects who specifically withdraw consent release of such information. All procedures and laboratory specimens or tests requested for evaluation following administration of the investigational product should be carried out when possible whether or not a subject continues to receive treatment according the protocol. The attempts and any reason(s) for missing data as a result of the withdrawal will be captured in the source.

Participating study sites will be trained on the importance of completing study follow-up procedures, and collecting the documentation required for missing data values. Any withdrawn subjects will not be replaced in this study.

4.4.1. Withdrawal from Study Medication

In the event a subject withdraws or is withdrawn from the study medication (eg, receives first injection and not second injection), the investigator will inform the Medical Monitor and the Sponsor immediately. If there is a medical reason for withdrawal, the subject will remain under the supervision of the investigator for protocol-specified safety follow up procedures. The IDMC will be notified.

It is imperative to obtain complete follow-up data (through Day 540 procedures) for all randomized subjects whether or not they receive their assigned treatment or have discontinued investigational product.

4.5. Stopping Criteria

4.5.1. Individual Subject Dosing Stopping Criteria

During the double-blind, active treatment phase subjects will have clinic visits at regular intervals. Dosing with blinded study medication (inclisiran and/or matching placebo) should be temporarily discontinued or stopped in subjects with:

1. Intolerable adverse events, or if the Investigator believes that continuing dosing will be detrimental to the subject's mental or physical health. This includes severe or serious reactions at the injection site and any anaphylactic type reactions.
2. Unexplained increases in transaminases (ALT or AST) or total bilirubin as follows:
 - a. ALT or AST >8xULN
 - b. ALT or AST >5xULN for more than 2 weeks
 - c. ALT or AST >3xULN and (total bilirubin >2xULN or INR >1.5)
 - d. ALT or AST >3xULN with the appearance of fatigue, nausea, vomiting, right upper quadrant pain or tenderness, fever, rash, and/or eosinophilia (>5%)

The investigator should evaluate to see if other causes for the laboratory abnormalities are immediately apparent, such as obstructive gall bladder or bile duct disease, viral or alcoholic hepatitis, malignancy involving the liver, congestive hepatopathy, other hepatotoxins or heritable disorders.

3. Unexplained creatine kinase (CK) values $>5 \times$ ULN confirmed by repeat test when the CK elevation is associated with muscle pain, muscle tenderness and/or muscle weakness, or new onset renal dysfunction.

In the case that study medication is permanently discontinued the subject will be asked to complete the remainder of the scheduled visits without receiving blinded study medication (inclisiran or placebo).

All trial subjects should be followed until all abnormalities return to normal or to the baseline state.

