6.3. Screening Period (Days –14 to –1)

All screening laboratory tests will be collected and shipped to the Central Laboratory, with the exception of urinalysis and pregnancy test, which will be done in-house at the participating institution's laboratory using the testing materials provided by the Central Laboratory. The results of all screening laboratory tests should be reviewed prior to enrollment. If results do not confirm subject eligibility or suggest any contraindication to treatment with inclisiran, and/or other required ancillary medication(s), the subject must not be enrolled.

The following procedures will be performed within 14 days prior to randomization:

- Informed consent
- Assessment of inclusion and exclusion criteria
- Demographics and medical history
- Pregnancy test (performed locally, using central laboratory supplies) (women of childbearing potential only)
- Physical examination (including height, weight, and waist circumference)
- Vital signs (blood pressure and heart rate) ([Section 7.1.3](#))
- 12-lead ECG
- Fasting lipid profile/biomarkers ([Section 7.2](#))
- Central clinical laboratory (limited serum chemistry, hematology and coagulation) ([Section 7.1.8](#))
- Urinalysis (performed locally, using central laboratory supplies)
- Previous and concomitant medications
- AE/SAE reporting (beginning from time of consent)
- Pharmacogenetics (stored samples, only if separate consent has been signed) ([APPENDIX C](#))

Central laboratory blood draws should be performed after all other screening tests have been confirmed. Results must be available before the start of investigational product injection on Day 1 to confirm subjects meet eligibility criteria ([Section 4.2](#) and [Section 4.3](#)). Please refer to [Section 7.1.8](#) and [Section 7.2](#) for details of laboratory tests performed during the screening period.

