6.6. Additional Dosing Visits (Days 90, 270, and 450)

Subjects will return on Day 90 for a second investigational product injection. Subsequent investigational product injections will be administered on Day 270 and Day 450.

The following assessments will be completed during these visits prior to investigational product administration:

- Pregnancy test (performed locally, using central laboratory supplies, if applicable) (women of childbearing potential only)
- Vital signs: blood pressure and heart rate ([Section 7.1.3](#))
- Fasting lipid profile/biomarkers ([Section 7.2](#))
- Collection and storage of serum samples for possible future use to detect the formation of ADA ([Section 7.1.8.8](#))
- Central clinical laboratory (limited serum chemistry) ([Section 7.1.8](#))
- Concomitant medication
- AE/SAE reporting

Administration of the investigational product is identical to Day 1 and is per [Section 5.1.1](#) and the Pharmacy Manual.

Subjects must be observed in the clinic for at least 30 minutes after injection.

Should a subject develop signs or symptoms of anaphylaxis on days when investigational product is injected, the investigator will need to collect a blood sample for tryptase within 30 minutes of the onset of anaphylaxis (or as soon as logically possible).

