7.1.8.2. Coagulation

Blood draws for coagulation will include:

- Prothrombin time (PT), international normalized ratio (INR), activated partial thromboplastin (aPTT).

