7.1.8.3. Chemistry

Blood draws for chemistry will be performed per the Schedule of Assessments ([Table 2](#)). Analysis will vary based on visit day as follows:

- **Full serum chemistry - Baseline (Day 1) and EOS (Day 540)**
AST, ALT, alkaline phosphatase (ALP), gamma glutamyl transferase (GGT), total bilirubin (TBIL), direct and indirect bilirubin, creatine phosphokinase (CPK), lactate, bicarbonate, uric acid, creatinine, urea (BUN), estimated glomerular filtration rate (eGFR), sodium, potassium, calcium, inorganic phosphate, chloride, albumin, total protein, glucose (fasting), glycated hemoglobin A1C (HbA1C), and tryptase (as required).
- **Limited serum chemistry - Screening, Days 90, 150, 270, 330, 450 and 510**
ONLY: AST, ALT, ALP, GGT, TBIL, CPK, creatinine, eGFR, fasting glucose, HbA1C (not at Day 150, 330 and 510) and tryptase (as required).

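### The dosing-stop rule and the laboratory schedule do not line up: INR and eosinophils are not scheduled at any repeat-dosing visit, and no laboratory review is required before a repeat injection

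*Protocol*

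**What the plan says.** Protocol section 4.5.1 lists when an individual's dosing is to be paused or stopped. Besides investigator judgement and intolerable events (criterion 1), it has four liver limbs and a CK criterion:

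- 2a: ALT or AST above 8 times ULN.
- 2b: "ALT or AST >5xULN for more than 2 weeks".
- 2c: "ALT or AST >3xULN and (total bilirubin >2xULN or INR >1.5".
- 2d: ALT or AST above 3 times ULN with any of a list of symptoms that ends "fever, rash, and/or eosinophilia (>5" per cent.
- 3: CK above 5 times ULN, "confirmed by repeat test when the CK elevation is associated with muscle pain" or related findings.

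INR belongs to the coagulation panel (7.1.8.2: "Prothrombin time (PT), international normalized ratio (INR), activated partial thromboplastin (aPTT"). Eosinophils come from the differential in the hematology panel (7.1.8.1).

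The dosing visits on Days 90, 270 and 450 carry "Central clinical laboratory (limited serum chemistry" (6.6). Section 7.1.8.3 restricts that panel to "ONLY: AST, ALT, ALP, GGT, TBIL, CPK, creatinine, eGFR, fasting glucose" plus HbA1c and, as required, tryptase. Day 30 (6.5) consists of anti-drug antibodies, concomitant medications and adverse events.

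For the first dose, 6.3 says of the screening tests: "Results must be available before the start of investigational product injection on Day 1 to confirm subjects meet eligibility criteria". Section 7.1.8 repeats this. Section 6.6 has no counterpart. SAP Table 1 and SAP sections 3.3 to 3.5 and 3.8.8 carry the same schedule, so the SAP does not fill the gap.

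**The concern.** Section 4.5.1 is the written safeguard against giving another dose to a subject with possible liver or muscle injury. It can serve that purpose only if the values it names exist, and have been looked at, when the next dose is decided. Two things raise doubt. Two of the named analytes are not scheduled at the visits where that decision is made. And for dose 2, no post-dose value of any analyte in the rule comes from an earlier scheduled visit.

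As written, a subject whose Day 90 sample meets a laboratory limb can receive dose 2 at that same visit without any breach of the protocol. Whether an INR or a differential is obtained after a raised ALT or AST is also left to each site, so the rule may be applied unevenly.

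**Working it through.** There is no stated figure to reproduce. The check sets the rule against the schedule.

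**Step 1. What is scheduled when** (Table 2; sections 6.4 to 6.8; panel contents in 7.1.8.1 to 7.1.8.3, where CK appears as CPK):

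| Visit | ALT/AST, bilirubin, CK | INR, differential |
|---|---|---|
| Day 1, before dose 1 | yes | yes |
| Day 30 | no | no |
| Day 90, dose 2 | yes | no |
| Day 150 | yes | yes |
| Day 270, dose 3 | yes | no |
| Day 330 | yes | no |
| Day 450, dose 4 | yes | no |
| Day 510 | yes | no |
| Day 540 | yes | yes |

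INR and the differential are scheduled at 0 of 3 repeat-dosing visits. They accompany ALT/AST at 2 of the 7 post-dose chemistry visits (Days 150 and 540), and at 1 of the 5 up to and including the last dose (Day 150).

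**Step 2. Age of the latest sample from an earlier visit.** Age = dose day minus day of the last earlier scheduled sample. The range moves both visits to the edges of their Table 2 windows (Day 1 has none; ±30 days for the others used here).

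| Dose | Chemistry | INR, differential |
|---|---|---|
| Day 90 | 90 − 1 = 89 days (59 to 119), pre-dose only | 89 days (59 to 119), pre-dose only |
| Day 270 | 270 − 150 = 120 days (60 to 180) | 120 days (60 to 180) |
| Day 450 | 450 − 330 = 120 days (60 to 180) | 450 − 150 = 300 days (240 to 360) |

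Before dose 2 there is therefore no post-dose value, from an earlier scheduled visit, for any analyte in the rule. A Day 30 antibody sample exists but does not feed the rule.

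**Step 3. Which limbs need the missing tests.** 2a and 2b use ALT/AST alone. 2c can be met through bilirubin and 2d through symptoms. Criterion 3 uses CK. INR or eosinophils decide the matter only when ALT/AST is above 3 times ULN, 2a and 2b are not met, bilirubin is at or below 2 times ULN, no listed symptom is present, and criterion 1 has not been invoked.

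**Step 4. Does the rule look beyond scheduled samples?** Nominal gaps between successive chemistry samples from Day 1 on are 89, 60, 120, 60, 120, 60 and 30 days. A limb that turns on more than 2 weeks (2b) and a CK repeat (3) are not served by those gaps, so the rule presupposes unscheduled testing.

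**Step 5. Is conditional testing written down?** It is for tryptase (as required), for urine microscopy after an abnormal dipstick (7.1.8.5) and for extra ECGs (7.1.6). It is not for an INR or a differential after a raised ALT or AST. Section 5.3.1 requires abnormal findings to be followed but names no test and does not tie follow-up to the next dose.

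**The case against.** A reader might infer that the rule cannot operate as written. The documents do not support that. INR is one of two alternatives in 2c, and eosinophilia is one of seven features in 2d. ALT, AST, bilirubin and CPK are in the panel at every dosing visit. Table 2 is a minimum schedule and bars no extra test: its footnote 4 allows additional laboratory work if needed during the observation after an injection, and SAP section 6.3.3 accommodates unscheduled visits. Section 4.5.1 itself asks the investigator to look for other causes and to follow abnormalities until they return to normal or to baseline. All of this stands, and it limits the point to a weakened rule.

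A reader might also infer that every Day 90 injection is given before the Day 90 result is known. That goes beyond the text. The sample is drawn before the injection, turnaround is not stated, and processing is deferred to a Laboratory Manual that is not part of these documents. The ±30-day window, and the exclusion of safety delays from mis-dosing in section 12.3, leave room to wait for a result. But the protocol leaves that room without requiring its use.

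The Day 1 requirement concerns eligibility, so it is not an exact parallel. It does show that the protocol states such a condition where one is intended.

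Multiplying the gaps by enrollment would count injections, not risk: the documents give no rate for the pattern in step 3. Nor does the prolonged LDL-C effect in section 1.2.2.2 show that harm would be irreversible. It describes efficacy, and section 1.2.1 reports mild, reversible enzyme rises in nonclinical studies.

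The IDMC's three-monthly reviews and the sponsor's ongoing review (8.6.2) are real safeguards, but they work at study level and do not decide an individual's next dose.

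**Conclusion.** The concern holds as a mismatch between the stopping rule and the schedule that weakens the rule. Three statements can be verified from the text: INR and the differential are scheduled at 0 of 3 repeat-dosing visits and, after Day 1, only at Days 150 and 540; the first post-dose sample for ALT/AST, bilirubin and CK is taken at the dose 2 visit itself; and no laboratory review is required before any repeat injection.

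That the Day 90 result is not in hand at injection is an inference that depends on an unstated turnaround. The sample ages assume that only scheduled samples are taken. The number of subjects affected cannot be derived from the documents. The point should be corrected because it concerns subject safety at repeat dosing. It does not bear on the efficacy analysis.

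**What to change.** Reconcile section 4.5.1 with Table 2 and sections 6.5, 6.6 and 7.1.8.3 in two respects:

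1. Make the tests named in 2c and 2d the tests that are available when the rule is applied, whether by schedule, by a stated reflex test, or by aligning the rule with the panel.
2. State in 6.6 which post-dose results must have been reviewed before each repeat injection.

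The clinical team decides which passage governs. No threshold, schedule or stopping rule is proposed here.

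The cost is protocol wording and a Laboratory Manual update. If the panel is the side that changes, a few tests are added at visits where blood is already drawn. No visit or subject is added. SAP Table 1 and SAP section 3 would need the same edit to stay consistent.

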5. TREATMENT OF SUBJECTS

5.1. Study Medications

5.1.1. Inclisiran

Investigational product (inclisiran) information is described in Table 1.

Table 1: Investigational Product

Product Name:	Inclisiran for Injection
Active ingredient	Inclisiran sodium
Dosage Form:	Solution for Injection
Unit Dose	Inclisiran sodium 300 mg/1.5 mL vial (equivalent to 284 mg inclisiran)
Route of Administration	SC use
Physical Description	Clear, colorless to pale yellow solution essentially free of particulates
Manufacturer	

Investigational product preparation: The pharmacist or qualified designee will prepare the investigational product under aseptic conditions to be administered to the subject on that day.

The procedure for preparing investigational product is provided in the Pharmacy Manual.

Investigational product administration: Subjects will be administered a single SC injection of 300 mg Inclisiran for Injection at predefined time points as described in the Schedule of Assessments (Table 2). Investigational product injection will be administered by qualified clinical study site staff under the supervision of the investigator or designee. The site of injection is the abdomen, alternating sides for each injection. Do not inject into areas of active skin disease or injury such as sunburns, skin rashes, inflammation, tattoos or skin infections.

5.1.2. Placebo

Placebo will be supplied by The Medicines Company to clinical study site as sterile normal saline (0.9% sodium chloride in water for injection) for SC injection. The placebo vials will be blinded and look identical to the inclisiran vials. Placebo will be administered as an SC injection in an amount matched to the doses within the active inclisiran arm (Table 1).

5.1.3. Packaging and Labeling

Investigational product (inclisiran for Injection and matching placebo) will be provided by the sponsor in a blinded fashion. All vials, inclisiran or placebo, will look identical. Medication labels will comply with regulatory requirements. The storage conditions for each medication provided will be described on the medication label.

The Inclisiran for Injection (SC use) is packaged in a glass vial (vials contain 300 mg of inclisiran sodium [equivalent to 284 mg of inclisiran per 1.5 mL]). The container closure system consists of a Type I glass vial, a Teflon-faced bromobutyl 13 millimeter stopper, and a flip off Truedge aluminum seal. Each vial will have a yellow shroud over the vial to maintain the blind.

5.1.4. Storage

Investigational product will be stored at room temperature (up to 25°C [77°F]) as specified in the Pharmacy Manual. Access should be strictly limited to the investigator, pharmacists, and their designees. No special procedures are required for the safe handling of Inclisiran for Injection.

5.1.5. Accountability

The investigator or designee must maintain an inventory record of investigational product (inclisiran/placebo) received and all administered to assure the regulatory authorities and the Sponsor that the new investigational product will not be dispensed to any person who is not a subject under the terms and conditions set forth in this protocol. Investigational product accountability forms and/or specific instructions can be found in the Pharmacy Manual.

[figure not shown]
The investigational product supplied for use in this study is to be prescribed only by the Principal Investigator or designated sub-investigators and may not be used for any purpose other than that outlined in this protocol.

During the study, all used investigational product containers (eg, empty vials) will be kept until the monitor has reviewed the accountability records.

All unused investigational product will be destroyed on site (or returned to the packaging and labeling facility for destruction) once the investigational product has been inventoried and the monitor has reviewed the accountability records. In the event that investigational product needs to be returned for any other reason, the site will receive a written request listing the investigational product lot number(s) to be returned and the reason for the return request.

5.1.6. Product Complaints

Sites are required to report any product complaints to The Medicines Company (MDCO) immediately but no later than 24 hours from the time of awareness, by phone or e-mail as follows:

Product Complaint: Is defined as any written, electronic, or oral communication that alleges deficiencies related to the identity, durability, reliability, quality, safety, effectiveness or performance of a product, after it is released for distribution (European Union [EU] DIR 2001/83/EC). (Derived from Ref United States [US] 21 CFR 211.198).

Technical Quality Complaint: A report of dissatisfaction with the product with regard to its efficacy, strength, integrity, purity, or quality; thus a potential failure to meet product specifications. Examples include:

- An indication that there is an unexpected physical change in the drug product such as discoloration, change in shape of the drug product, presence of particulates or any other physical change that might indicate contamination, a manufacturing defect or any other event that might indicate a compromise in product quality.
- An indication that the content does not meet its labeled volume, count, etc.
- An indication that there is an unexpected physical change in any part of the container (this includes the bottle, any part of the seal, the cap or the label).
- An indication that the product is mislabeled.
- An indication that there is an unexpected physical change of the product or container once the product is diluted or reconstituted (the container includes the vial, bag, intravenous line, syringe or any other item that is in contact with the product).
- An indication that the product is falsified, tampered with, or adulterated.
- An indication that the product did not meet its pharmacologic effect, ie, lack of efficacy.
- Medical Device Incidents.

5.2. Concomitant Medications

5.2.1. Prohibited Concomitant Medications

The following medications/treatments are not permitted to be added during the study:

- Medications prescribed to lower LDL-C (eg, statins, ezetimibe, lomitapide, mipomersen, niacin, colesevelam, bile acid absorption inhibitors, monoclonal antibodies directed towards PCSK9).
- Any medication taken for the purpose of lipid lowering, including over-the-counter or herbal therapies.

5.2.2. Permitted Concomitant Medications

The following medications/treatments are permitted during the study:

- Hormone replacement therapy
- Lipid-lower medications; subjects already on a stable (≥ 30 days before screening) lipid-lower medications (such as statins and/or ezetimibe) should remain on the dose that they have received during participation in the original protocol unless clinically indicated

- Prescription medications prescribed to treat preexisting medical conditions such as diabetes and hypertension
- Prescription or nonprescription medications, when necessary to treat an AE, and at the discretion of the investigator

